11.1 Adverse Event Definition

An adverse event (also referred to as an adverse experience) can be any unfavorable and unintended sign (e.g., an abnormal laboratory finding), symptom, or disease temporally associated with the use of a drug, and does not imply any judgment about causality. An adverse event can arise with any use of the drug (e.g., off-label use, use in combination with another drug) and with any route of administration, formulation, or dose, including an overdose.

11.2 Recording of Adverse Events

All adverse events will be recorded on a subject specific AE log. The AE log will be maintained by the research staff and kept in the subject's research chart.

Subjects enrolled in Group 2 will have pre-enrollment adverse events recorded, if they are related to Biktarvy following their switch from previous antiretroviral therapy.

11.3 Reporting of AE to WCM IRB

All AEs occurring on this study will be reported to the IRB according to the IRB policy, which can be accessed via the following link:
http://researchintegrity.weill.cornell.edu/forms_and_policies/forms/Immediate_Reporting_Policy.pdf.

11.4 Reporting of SAE to IRB

All SAEs occurring on this study will be reported to the IRB according to the IRB policy, which can be accessed via the following link:
http://researchintegrity.weill.cornell.edu/forms_and_policies/forms/Immediate_Reporting_Policy.pdf.

11.5 Reporting of SAE to Gilead

Institution will send Gilead copies of any and all serious adverse event reports filed with the FDA or other applicable regulatory authorities, as well as copies of any correspondence with the FDA or other applicable regulatory authorities, regarding any and all serious adverse events, irrespective of association with the Study Drug(s) in the course of the Clinical Trial, within 3 business days of such report or correspondence being sent to the FDA or other applicable regulatory authorities.

11.6 AE/SAE Follow Up

All SAEs and AEs reported during this study will be followed until resolution or until the investigator confirms that the AE/SAE has stabilized and no more follow-up is required. This requirement indicates that follow-up may be required for some events after the subject discontinues participation from the study.

12. Data and Safety Monitoring Plan (DSMP)

The WCM DSMB will be used for this investigator-initiated study. The following information will be submitted to the WCM DSMB every 6 months from the time of the first enrollment:

Laboratory results

- T-lymphocytes, HIV viral load: From Day 1, Week 4, Week 12, Week 24, Week 36, Week 48, 3-month Follow-up, and 6-month Follow-up
- Select clinical safety labs¹: From Day 1 and all visits from Week 4 through 6-month Follow-up

- BUN, creatinine: From Days 3 through Day 22, and if needed at additional time points, as per investigator
- Tacrolimus levels: All time points
- Any HIV-resistance testing needed, as per investigator

¹Clinical Safety Labs include: CBC, complete metabolic panel, urinalysis, eGFR

Adverse Events and Stopping Rules

The following adverse events will be submitted to the WCM DSMB and may cause the subject to terminate protocol treatment:

1. Severe drug reaction, including rash or fever (as determined by the PI)
2. Inability to control tacrolimus levels, as defined by the primary renal transplant provider, which may lead to renal graft failure
3. ALT or AST > 5 x ULN
4. Virologic failure, as determined by the Principal Investigator, which would be defined as: On-treatment HIV-1 RNA ≥ 50 copies/mL twice sequentially, separated by 4-6 weeks
5. Development of documented resistance to BIC/FTC/TAF

Renal dysfunction requiring evaluation is defined as a decrease in creatinine clearance to CrCl < 30 mL/min. The evaluation of renal dysfunction will be completed by the primary renal transplant team, in conjunction with the PI.

If the CrCl is below 30 mL/min, the BIC/F/TAF will be held and an evaluation will be performed by the primary renal transplant physician in conjunction with the PI. The evaluation of the cause will be explored by the primary renal transplant physician in conjunction with the PI. The patient will be discontinued from the study at the discretion of the PI, after discussion with the primary renal transplant physician, if deemed necessary.

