6.1 Schedule of Assessments*

Activity	D 1	D 3	D 8	D 15	D 22	W 4	W 8	W 12	W 16	W 24	W 32	W 36	W 48	FU – M3	FU – M6	UV ^k	
Visit Window (Days)	±1	±3				±7											
Informed consent	X ^a																
Inclusion/Exclusion Criteria	X																
Research study visit, including weight	X	X ⁱ	X ^j	X ^j	X ^j	X	X	X	X	X	X	X	X	X	X	X	
Physical exam	X					X ^b		X ^b		X		X ^b	X	X ^b	X ^b	X ^b	
Questionnaire booklet administration	X																
Questionnaire completion ^c						X		X		X		X	X	X	X	X	
Dispense study medication	X										X						
T-lymphocytes, HIV viral load	X					X		X		X		X	X	X	X	X	
HIV-resistance testing		As needed, as per investigator ^d															
Tacrolimus level	X	X ⁱ	X ^j	X ^j	X ^j	X	X	X	X	X	X	X	X	X	X	X	
BUN, creatinine		X ⁱ	X ^j	X ^j	X ^j	As needed, as per investigator ^e											
Clinical Safety Labs ^f	X					X	X	X	X	X	X	X	X	X	X	X	
TAF levels, intracellular (dried blood spot) ^g								X		X		X	X		X	X	
TAF levels, intracellular (PBMC) ^h								X									
Pharmacokinetics ⁱ								X									

Abbreviations: D = Day; W = Week; M = Month; FU = Follow-up; UV = Unscheduled Visit

*If services outside of the study (standard of care, or "SOC") are completed for a patient during the study period, only the research-related tests and procedures will be billed to the study. SOC tests and procedures are expected throughout the study period for this population.

^a Informed consent may be obtained up to 2 months before D1. Subjects enrolled into Group 2 will begin the study schedule at the Day 1 visit and will then be inserted into the Schedule of Assessments at the discretion of the Principal Investigator based on stability of the subject's HIV viral load and tacrolimus levels.

^b If there are complications, as deemed by the investigator, a physical exam will be conducted at this time point. If institutional restrictions limit outpatient visits, the most recent physical exam completed by the primary care physician will be used to avoid direct contact or exposure of patients.

^c Questionnaires may be completed by phone or returned by mail, if institutional restrictions limit outpatient visits.

^d HIV resistance testing will be performed if there are two consecutive breakthrough HIV viral loads >50 copies/mL, spaced 4-6 weeks apart.

^e Additional BUN and/or creatinine labwork may be drawn at these timepoints, if deemed necessary for safety purposes by the investigator.

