^f Clinical Safety Labs include: CBC, complete metabolic panel, urinalysis, eGFR, urine protein/creatinine ratio, urine albumin/creatinine ratio, phosphorus, retinol binding protein, and beta 2 microglobulin. For subjects enrolled in Group 2, all standard of care lab values and concomitant medications will be collected for 60] days prior to the Biktarvy switch date and the duration of Biktarvy therapy will also be recorded.

^g Three samples will be collected on W12 at 0, 4, and 24 hours (the 24 hour time point is optional, if feasible), and 1 sample will be collected at visits W24, W36, and W48, and FU – M6. Stored samples will be sent to [name] at the University of Colorado's Antiviral Laboratory.

^h Three samples will be collected on W12 at 0, 4, and 24 hours (the 24 hour time point is optional, if feasible). Stored samples will be sent to [name] at the University of Colorado's Antiviral Laboratory.

ⁱ Six samples will be collected on W12 at 0, 0.5, 1, 2, 4, and 24 hours (the 24 hour time point is optional, if feasible). Pharmacokinetic testing for Group 2 subjects will be completed once the subject's tacrolimus levels are stable as per the Principal Investigator for 2-4 weeks.

^j The study visits and bloodwork at these timepoints will be optional, to be completed as needed, as per the investigator.

^k If a subject needs to stop treatment as per the Data and Safety Monitoring Plan (Section 12), the subject will be seen as soon as possible for an Unscheduled Visit and will continue to be followed for the duration of the study as per the Schedule of Assessments for non-terminated patients.

Informed consent will be obtained on Day 1 or up to 2 months prior to Day 1, before starting the study (switch day) (Section 6.1).

Patients will have bloodwork completed throughout the study, as shown in the Schedule of Assessments (Section 6.1).

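### Virologic failure and the resistance-testing trigger need two raised viral loads 4-6 weeks apart, but for subjects switched at Day 1 no consecutive on-treatment pair in the schedule is nominally that close, and nothing in the plan ensures a repeat sample

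*Combined protocol and SAP*

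**What the plan says.** Section 12 lists five events that go to the DSMB and may end protocol treatment. Item 4 is virologic failure, which the principal investigator determines and which is defined as "On-treatment HIV-1 RNA ≥ 50 copies/mL twice sequentially, separated by 4-6 weeks". Item 5 is documented resistance.

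In Section 6.1 the resistance-testing row reads "As needed, as per investigator". It carries footnote d, under which testing is done after "two consecutive breakthrough HIV viral loads >50 copies/mL, spaced 4-6 weeks apart".

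Section 12 lists the viral-load time points as "T-lymphocytes, HIV viral load: From Day 1, Week 4, Week 12, Week 24, Week 36, Week 48, 3-month Follow-up, and 6-month Follow-up". The schedule in Section 6.1 shows the same visits and adds the unscheduled visit. Weeks 8, 16 and 32 are study visits with safety labs and tacrolimus levels but no viral load.

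The unscheduled visit, to be held promptly, is described in footnote k and again in the text below the schedule: "If a subject needs to stop treatment as per the Data and Safety Monitoring Plan (Section 12), the subject will be seen".

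Section 6.1 identifies Day 1 as the day of the switch. Group 2, described in Section 3.1, had switched before being identified for the study. Footnote a states "Subjects enrolled into Group 2 will begin the study schedule at the Day 1 visit", after which the investigator decides where in the schedule they continue.

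**The concern.** The failure definition and the resistance trigger both depend on an interval that the viral-load schedule does not produce for subjects switched at Day 1. The one extra visit that carries a viral load is described for a subject who already needs to stop treatment. A first raised value is not a stopping event under item 4, because item 4 needs two. As described, that visit follows the decision which a second sample would inform.

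At stake is how a statement that no subject had confirmed failure or emergent resistance should be read. Section 10.1 gives sustained suppression throughout the study as the first expected outcome, so such a statement is likely to appear in the report. If the data could hardly satisfy the definition, a zero count says little about the drug. The two cut-offs add a small mismatch: a value of exactly 50 copies/mL counts toward failure but not toward the testing trigger.

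**Working it through.** The plan gives no figure to reproduce here. The check compares the required interval with the scheduled visits.

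**Inputs**
- Required separation: 4-6 weeks, that is 28-42 days (Section 12 item 4; footnote d).
- Viral-load visits: Day 1, Weeks 4, 12, 24, 36 and 48, and follow-up Months 3 and 6 (Sections 6.1 and 12).
- Assumption: follow-up months run from Week 48, at about 13 weeks (91 days) per three months.
- Assumption: the window row, which is broken in the text available, means ±1 day at Day 1 and ±7 days from Week 4.

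**Formula**
- Nominal gap = later visit day − earlier visit day, with Day 1 set to 0 and Week w set to 7w.
- Range = nominal gap ± (sum of the two windows).
- The last column counts whole-day combinations of the two visits that fall 28-42 days apart.

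| Consecutive pair | Nominal gap (weeks) | Range with windows (weeks) | Combinations at 28-42 days |
|---|---|---|---|
| Day 1 to Week 4 | 4 | 2.9 to 5.1 | 24 of 45 |
| Week 4 to Week 12 | 8 | 6 to 10 | 1 of 225 |
| Week 12 to Week 24 | 12 | 10 to 14 | 0 of 225 |
| Week 24 to Week 36 | 12 | 10 to 14 | 0 of 225 |
| Week 36 to Week 48 | 12 | 10 to 14 | 0 of 225 |
| Week 48 to Month 3 | about 13 | 11 to 15 | 0 of 225 |
| Month 3 to Month 6 | about 13 | 11 to 15 | 0 of 225 |

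**Reading the table**
- *Subjects switched at Day 1.* The Day 1 sample is the switch-day baseline, so the first row is not an on-treatment pair. Of the four on-treatment pairs to Week 48, 0 qualify nominally. The single qualifying combination for Week 4 to Week 12 has Week 4 seven days late and Week 12 seven days early: 56 − 14 = 42 days.
- *Group 2.* Day 1 is on treatment, so Day 1 to Week 4 can qualify if the investigator places the next visit at Week 4.
- *Follow-up.* Neither follow-up pair qualifies, whether or not subjects are still on treatment then.

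**Worked case.** A subject at ≥50 copies/mL at Weeks 24 and 36 has two sequential raised values 84 days apart. That exceeds 42 days, so item 4 is not met. Footnote d is not met either, for the same reason.

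**Size.** With 20 planned subjects (synopsis), one unlabelled case is 1/20 = 5%. With the eighteen of Section 3.1 it is 1/18 = 5.6%. The only rate in the documents is 3 of 282 at ≥50 copies/mL at Week 48, in the switch trial cited in Section 10.1. If that applied here, the expected number is 20 × 3/282 = 0.21. This is an assumption, since the plan does not describe that trial's population as transplant recipients.

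**The case against.** The strongest reply is that a 4-6 week interval set beside a mainly 12-week schedule naturally implies a repeat test after a first raised value. The plan leaves room for one:
- Failure is for the principal investigator to determine.
- Resistance testing is as needed.
- Standard-of-care tests are expected throughout the study.
- Footnote k does not say that unscheduled visits are only for subjects who are stopping.
- Weeks 8 and 16 fall 4 weeks after Weeks 4 and 12, so a repeat could be added to an existing draw.

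This stands as far as it goes. A reader might infer that failure can never be confirmed, or that an unscheduled viral load is barred for anyone else. The documents support neither inference. What they lack is any passage that calls for the second sample or times it. No study visit is scheduled 4-6 weeks after Week 24, 36 or 48.

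A reader might also infer that rebound would be hidden or the efficacy result biased. That does not follow. The primary efficacy endpoint is the proportion below 50 copies/mL at Week 48, which needs no confirmation, so a subject raised at that visit is not counted as suppressed. Every scheduled viral load goes to the DSMB whether or not failure is confirmed. Confirmed failure and resistance are not listed primary or secondary endpoints. Documented resistance is also its own stopping item and does not require item 4.

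Finally, few cases are expected at the cited rate, and the cut-off difference matters only for a result of exactly 50. Both points limit the scale but do not remove the inconsistency.

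**Conclusion.** The point holds as an inconsistency between a definition and the schedule meant to feed it. For subjects switched at Day 1, 0 of 4 consecutive on-treatment pairs to Week 48 are nominally 4-6 weeks apart, and only one edge combination of Week 4 and Week 12 can reach 6 weeks. Group 2 may have one qualifying pair, at the investigator's discretion. A second value within the interval may be obtained in practice, but nothing in the plan ensures it. A zero count of confirmed failures or of resistance would therefore be hard to interpret.

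The effect is confined to the failure label, the stopping rule that uses it and the resistance-testing trigger. The range calculation rests on the assumed reading of the window row, and the follow-up gaps on counting months from Week 48. The nominal result to Week 48 needs neither assumption. It is worth correcting because the change is cheap, but it does not threaten the primary analysis.

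**What to change.** Reconcile Section 12 item 4, footnotes d and k and the viral-load schedule, so that the definition and the planned sampling agree. State one cut-off in place of ≥50 and >50. How they are reconciled is a clinical decision for the sponsor and investigator.

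In the analysis, report confirmed failure as defined. Add one line listing every subject with two consecutive on-treatment values ≥50 copies/mL regardless of the gap, with the dates and whether resistance testing was done. In this table line, ≥50 is simply the complement of the primary endpoint. State alongside it how many subjects with a first raised value had a second value within 4-6 weeks, so that a zero count can be judged.

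The cost is a wording change and one extra table line from data already collected. The drawback is that the line may count some subjects whose raised values were not confirmed within 4-6 weeks, so it should be labelled separately from confirmed failure.

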Pharmacokinetic (PK) studies will be assessed at Week 12 when the renal function is stable (decided by PI). Intracellular TAF levels by dried blood spot will be collected during the Week 12 visit at 0, 4, and 24 hours post-dose (the 24 hour time point is optional, if feasible). Additionally, 1 sample will be collected at Week 24, Week 36, Week 48, Month 6 Follow-up. Over the course of the study, 7 dried blood spot collections will be completed per patient. Intracellular TAF levels by PBMC will be collected once during the Week 12 visit at 0, 4, and 24 hours post-dose (the 24 hour time point is optional, if feasible). An intensive pharmacokinetic day will take place at the Week 12 visit, during which up to 7 samples will be collected at 0, 0.5, 1, 2, 4 and 24 hours post-dose (the 24 hour time point is optional, if feasible). This bloodwork is outlined in Section 6.1. Bloodwork for the intracellular TAF level testing and pharmacokinetic testing will be stored and sent to [name] at the University of Colorado's Antiviral Laboratory. (14-16)

A health-related quality of life questionnaire (Appendix) will be administered to each patient to assess satisfaction with a one pill regimen as well as adverse events (Section 6.1).

If a subject needs to stop treatment as per the Data and Safety Monitoring Plan (Section 12), the subject will be seen as soon as possible for an Unscheduled Visit and will continue to be followed for the duration of the study as per the Schedule of Assessments for non-terminated patients.

If services outside of the study (standard of care, or "SOC") are completed for a patient during the study period, only the research-related tests and procedures will be billed to the study, regardless of study visit date overlap. SOC tests and procedures are expected throughout the study period for this population.

Sample Collection

Samples include plasma and peripheral blood mononuclear cells (PBMC). Blood is collected in EDTA tubes for plasma separation. CPT vacutainers are used to isolate PBMC, which are counted with an automated countess cytometer (Invitrogen™, Thermo Fisher Scientific Corporation, Carlsbad, CA) and lysed. BIC, F, and TAF in plasma are assayed using a validated LC/MS/MS methodology with a lower limit of quantification (LLOQ) of 10 ng/mL (16).

7. Study Intervention

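### After a CrCl <30 hold, Section 12 allows exit from the study where Section 6.1 requires continued follow-up; taken literally, week-24/48 renal and later rejection data can be lost because of a poor renal outcome

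*Combined protocol and SAP*

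**What the plan says.** Section 12 describes two kinds of consequence.

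- **Five numbered events** (severe drug reaction, uncontrolled tacrolimus, raised transaminases, virologic failure, resistance) are introduced with: "The following adverse events will be submitted to the WCM DSMB and may cause the subject to terminate protocol treatment". The consequence is a treatment stop.
- **CrCl <30 mL/min** is dealt with separately, after that list. The drug is held, the renal transplant physician and the PI look for the cause, and then: "The patient will be discontinued from the study at the discretion of the PI, after discussion with the primary renal transplant physician, if deemed necessary".

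Section 6.1 has a follow-up rule, given in footnote k and repeated in the text. Its condition is: "If a subject needs to stop treatment as per the Data and Safety Monitoring Plan (Section 12"). Its consequence is an Unscheduled Visit as soon as possible, after which the subject "will continue to be followed for the duration of the study as per the Schedule of Assessments for non-terminated patients".

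The Synopsis places the renal biomarkers (primary objective 4) and the incidence of graft rejection (secondary objective 1) at weeks 24 and 48. Section 10.1 plans descriptive statistics and has no rule for a subject without a week-48 value.

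**The concern.** The trigger for leaving is itself a renal outcome, and two of the study's objectives are renal. A subject taken off the study after CrCl <30 would contribute nothing further to the week-24/48 biomarker summaries, and a first rejection occurring after exit would not be captured by any scheduled visit. Missingness would then depend on how badly the graft was doing, and a summary of those still present would lean towards the preserved renal function that Section 10.1 expects.

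**Working it through.** There is no stated figure to reproduce: the sample size rests on feasibility and no renal threshold or test is planned. The check is a comparison of texts, followed by a count from the schedule.

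**1. Which rule applies at CrCl <30?**

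| | Section 12, CrCl rule | Section 6.1, footnote k and text |
|---|---|---|
| Trigger | CrCl <30 mL/min, drug already held | Treatment stop under Section 12 |
| Consequence | Possible exit from the study, at PI discretion | Unscheduled Visit, then the full schedule |
| Mentions leaving the study? | Yes | No |

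A subject whose drug is stopped for CrCl <30 meets both triggers, and the consequences differ. Section 11.6 separately recognises that a subject can leave the study, so exit is a status distinct from a treatment stop. No sentence ranks the two rules.

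**2. What stays and what goes if the exit is literal?**

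- *Stays:* the renal event as an adverse event ("All adverse events will be recorded on a subject specific AE log"); its follow-up to resolution or stabilisation, since Section 11.6 adds "This requirement indicates that follow-up may be required for some events after the subject discontinues participation from the study"; and all values taken before exit.
- *Stays if footnote k is triggered:* the Unscheduled Visit. Its column in the schedule has tacrolimus, viral load and the Clinical Safety Labs, which under footnote f include "urine protein/creatinine ratio, urine albumin/creatinine ratio, phosphorus, retinol binding protein, and beta 2 microglobulin". The objective-4 measures would therefore be taken near the event.
- *Not secured:* scheduled biomarkers falling after exit, and a rejection that first arises after exit.

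**3. How much of the schedule is at risk?**

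Scheduled Clinical Safety Lab sets in Section 6.1, leaving out the Unscheduled Visit: D1, W4, W8, W12, W16, W24, W32, W36, W48, M3, M6 = 11.

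| Exit just after | Sets forgone | Target weeks among them |
|---|---|---|
| W12 | W16, W24, W32, W36, W48, M3, M6 = 7 of 11 | 24 and 48 |
| W24 | W32, W36, W48, M3, M6 = 5 of 11 | 48 |
| W36 | W48, M3, M6 = 3 of 11 | 48 |

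These counts are for a subject on the full schedule. Group 2 subjects join at a point chosen by the PI, so theirs may differ.

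**4. How large could the effect be?**

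The documents give no rate of CrCl <30, no baseline distribution and no exit rate, so what follows rests on assumptions.

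- *Weight of one subject:* 1/20 = 5.0% (1/18 = 5.6% with the eighteen given in Section 3.1).
- *Chance that the rule is reached at all:* 1 − (1 − p)^20. For an assumed per-subject risk p of 5%, 1 − 0.95^20 = 64%; for 10%, 1 − 0.90^20 = 88%. This is the chance of at least one CrCl <30 event, not of an exit. Section 4.3 sets the entry limit at the same 30 mL/min, so a subject can enrol just above the hold threshold.
- *Shift in mean week-48 eGFR change:* if k of 20 leave, their unseen change is d, and the others average 0, the observed mean is 0 and the full mean is k × d/20. For d from −20 to −30 mL/min: k = 1 gives −1.0 to −1.5; k = 2 gives −2.0 to −3.0; k = 4 gives −4.0 to −6.0. If renal function recovers after the hold, the shift shrinks accordingly.

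**The case against.** The strongest reply is that footnote k already settles the matter. It refers to Section 12 as a whole, not only to the five numbered events. Nobody can be discontinued under the CrCl rule without stopping BIC/F/TAF, and the follow-up instruction is firm and given twice. On that view the Section 12 sentence is loose wording for stopping study drug and no data are lost. This is a fair reading and may be the intended one. It does not remove the conflict, because the drug has already been held when the sentence applies, so a site could naturally take the further step to mean leaving the study.

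Three narrower points stand. First, a rejection that caused the fall in CrCl should be found during the evaluation, before any exit, and followed under Section 11.6; only a new, later rejection is exposed. Second, if the Unscheduled Visit takes place, the renal state near the event is documented by more than an adverse-event entry, although this does not replace a week-48 value. Third, the study is a descriptive pilot, and renal biomarkers are an objective but not among the three listed primary endpoints.

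**Conclusion.** The conflict is real and worth correcting as a cheap improvement. Followed literally, Section 12 lets the loss of remaining week-24/48 biomarkers and of later rejections depend on a poor renal outcome, with no rule in Section 10.1 for the gaps. The size is unknown, and the direction (too favourable) assumes that those who leave would have had worse later values than those who stay.

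A reader might infer more than the documents support:

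- *That the plan removes every subject who reaches CrCl <30, or hides the renal event.* It does neither. Exit is discretionary, and the event stays in the adverse-event record.
- *That the week-48 HIV-RNA endpoint needs a new counting rule for subjects off drug.* The conflict concerns renal and rejection follow-up. Counting such subjects as not suppressed would turn that endpoint into a composite, and nothing here calls for it.
- *That the shorter laboratory list sent to the DSMB adds to the loss.* Section 12 presents it as a selection. What the DSMB receives does not alter what Section 6.1 collects.
- *That a distortion of rejection incidence can be stated.* The documents offer no basis for the number of subjects lost or of rejections missed.

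**What to change.** Replace the Section 12 sentence with: *The PI, having consulted the primary renal transplant physician, may stop BIC/F/TAF permanently; the subject then remains in follow-up under Section 6.1 footnote k unless consent is withdrawn.* In Section 10.1, state that these subjects are included in the week-24/48 renal and rejection summaries, and report how many had BIC/F/TAF held or stopped for CrCl <30.

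The PI's control over the drug is unchanged, and if a treatment stop was always meant, the edit only says so. The cost is a few extra visits or draws per affected subject and a possibly less favourable renal summary. Section 6.1 expects standard-of-care tests during the study but does not list them, so retinol binding protein and beta-2 microglobulin may need a study draw.
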